# Analytical Treatment Interruption (ATI)

Various laboratory-based assays measuring the frequency of infected CD4+ T cells carrying HIV proviral DNA and/or replication-competent virus and HIV-specific immune responses have been used to assess efficacy of immune-based therapies. To date, none of the assays are clinically validated to predict actual antiviral efficacy *in vivo*. Thus, ATI has been used to evaluate the antiviral efficacy of immune-based therapies by testing the ability of these interventions to blunt or prevent the viral rebound that occurs following interruption of ART. The use of ATI in the design of this study (Group 1) is the only way to determine if administration of 3BNC117 and 10-1074 results in clinically relevant antiviral activity in antiretroviral-treated individuals, as evidenced by an attenuated or absent plasma viral rebound following interruption of ART. ATI, with frequent clinical and laboratory monitoring along with strict criteria for re-initiation of ART, is a safe and acceptable strategy to evaluate the efficacy of 3BNC117 and 10-1074 in this population of antiretroviral-treated HIV-infected adults. This is supported by the results from current and prior studies of immune based therapy using ATI to assess virologic efficacy, as well as a subgroup analysis of the SMART study.

## 2 STUDY OBJECTIVES

# 2.1 Primary Objective

To evaluate safety and tolerability of multiple doses of 3BNC117 combined with 10-1074 in HIV-infected individuals.

# 2.2 Secondary Objective

To evaluate the antiviral effect of combination therapy with 3BNC117 and 10-1074.

# 2.3 Exploratory Objectives

- To investigate whether 3BNC117 and 10-1074 -mediated suppression of HIV replication in the absence of ART allows the development of anti-HIV immunity (i.e., CTL response).
- To investigate the capacity of 3BNC117 and 10-1074 to neutralize replication-competent HIV prior to and following administration of the study drugs.
- To examine and characterize ex vivo 3BNC117 and 10-1074-escape mutants that might develop during the study.

#### 3 STUDY DESIGN

# 3.1 Description of the Study Design

The proposed trial will be a triple-arm study to examine the effect of 3BNC117 combined with 10-1074 in two groups of HIV-infected individuals. In Group 1, 30 individuals who began ART during primary HIV-1 infection will be randomized 1:1 to treatment with 3BNC117 plus 10-1074 or normal saline placebo. Study staff and participants will be blinded to Group 1 treatment assignments. Efficacy will be measured in this group by comparing the number of subjects in the treatment and placebo arm who meet criteria to restart ART during the ATI-treatment phase of the study (weeks 0-28).

For study Group 2, up to 15 viremic individuals not taking ART will receive 3BNC117 combined with 10-1074. Efficacy will be measured in this group by the proportion of subjects in whom mAb treatment is able to suppress plasma viremia during the treatment phase (weeks 0-28). Study subjects will receive infusions of 3BNC117 (30mg/kg) and 10-1074 (30mg/kg) or placebo (Group 1) at study days 0, Week 2, Week 4, and every four weeks thereafter for up to 24 weeks (Figure 1).

## Analytical treatment interruption (ATI)

After study day 3, all subjects in **Group 1** will stop ART to determine if treatment with 3BNC117 and 10-1074 can prevent plasma viral rebound. Individuals taking non-nucleoside reverse transcriptase inhibitors (NNRTIs) will switch to a protease or integrase inhibitor-based regimen at least 2 weeks prior to week 0 to ensure that the washout period of antiretroviral agents is roughly equal. During the ATI/Treatment phase of the study, HIV RNA levels and CD4+ T cell counts will be monitored every 2 weeks.

Group 1 subjects will be instructed to restart ART if they meet one or more of the following criteria during the ATI phase:

[figure not shown]
- A confirmed >30% decline in baseline CD4+ T cell count or an absolute CD4+ T cell count <350 cells/mm^3 that is associated with a HIV RNA level >40 copies/ml.
- A sustained (>4 weeks) HIV RNA level of >1,000 copies/mL
- Any HIV-related syndrome (e.g. acute retroviral syndrome, opportunistic infection)
- Pregnancy

Subjects who meet one or more of the above criteria during the ATI/Treatment Phase will not receive additional antibody/placebo infusions and enter the follow-up phase (Figure 1). Subjects who have not met criteria to restart ART by week 28 may continue the ATI and have HIV RNA levels and CD4+ T counts monitored every 2 weeks until they either meet criteria to restart ART or reach study week 64 (see Section 6.4).

Subjects in **Group 2** will have their plasma viremia and CD4+ T counts monitored every 2 weeks and will be removed from the treatment phase of the study if they meet any of the following criteria:

- A confirmed >30% decline in baseline CD4+T cell count or an absolute CD4 cell count <350 cells/mm^3
- A sustained (>4 weeks) 0.5log10 increase in baseline HIV RNA level
- Opportunistic infection
- Pregnancy

Figure 1: Study Outline

\* Placebo for Group 1 only

# 3.2 Study Endpoints

# 3.2.1 Primary Endpoint

The rate of occurrence of grade 3 or higher AEs, including SAEs, that, per standard criteria (see safety Section 12.3.1) are probably or definitely related to the test article.

# 3.2.2 Secondary Endpoints

Difference between the treatment and placebo arms in the number of subjects in study Group 1 who experience rebound of plasma viremia and meet criteria to restart ART prior to study week 28.

# 3.2.3 Exploratory Endpoint

Number of subjects in study Group 2 who achieve suppression of viremia to <40 copies/ml by study week 28.

## 4 STUDY POPULATION

#### 4.1 Recruitment Plan

Subjects will be recruited from existing cohorts of individuals participating in National Institute of Allergy and Infectious Diseases (NIAID) protocols 09-I-0030 and 02-I-0202 who meet the Inclusion/Exclusion Criteria. Additional local and regional recruitment will be done using direct mailing to infectious disease physicians, internet ad campaigns, social media outlets, print ads, and from local clinics via the NIAID patient recruitment contract with Matthews Media Group.

# 4.2 Subject Inclusion Criteria

General Inclusion Criteria for both Groups

\*\*Analytical Treatment Interruption

- 1. Age 18-65 years old.
- 2. HIV-1 infection and clinically stable.
- General good health and has an identified primary health care provider for medical management of HIV infection and is willing to maintain a relationship with a primary health care provider for medical management of HIV infection while participating in the study.
- 4. CD4+ T cell count >450 cells/mm^3 at screening.
- 5. Laboratory values within pre-defined limits at screening:
  - a. Absolute neutrophil count >1.000/mm^3.
  - b. Hemoglobin levels >10.0 g/dL for men and >9.0 g/dL for women.
  - c. Platelet count >100,000/mm^3.
  - d. Estimated or a measured glomerular filtration rate >60 mL/min/1.73m² as determined by the National Institutes of Health (NIH) Clinical Center laboratory.
  - e. AST and ALT levels of <2.5 x upper limit of normal (ULN), direct bilirubin within the normal range for the NIH Clinical Center laboratory.
- 6. Willingness to have samples stored for future research.

# Inclusion criteria specific for Group 1

- 7. Institution of ART within 12 weeks of being diagnosed with primary HIV-1 infection
- 8. Primary HIV-1 infection is defined as meeting at least one of the following criteria:
  - a. Detectable plasma HIV-1 RNA levels of >2000 copies/mL with a negative result from an HIV-1 EIA, or
  - Positive result from an HIV-1 EIA with a negative or indeterminate result from an HIV-1 western blot or another confirmatory antibody test that subsequently evolves to a confirmed positive result, or
  - c. Negative result from an HIV-1 EIA within the past 4 months and HIV-1 RNA levels of >400,000 copies/mL, in the setting of a potential exposure to HIV-1.
  - d. Negative result from an HIV-1 EIA within 6 months prior to a positive result from an HIV-1 EIA and an HIV-1 western blot or another confirmatory antibody test.
  - e. Presence of low level of HIV antibodies as determined by having a positive EIA or a positive Western blot with a non-reactive detuned EIA according to a serologic testing algorithm for recent infection.
- 9. Documentation of continuous ART treatment with suppression of plasma viral level below the limit of detection for ≥1 years. Individuals with "blips" (i.e., detectable viral levels on ART) prior to screening may be included provided they satisfy the following criteria:
  - a. The blips are <400 copies/mL, and
  - b. Succeeding viral levels return to levels below the limit of detection on subsequent testing.

- 10. Willingness to undergo ATI
- 11. Willingness for both male and female subjects to agree to use barrier protection methods or abstinence during the ATI phase of the study to decrease the risk of HIV transmission.

# Inclusion criteria specific for Group 2

- 12. No ART within 24 months of screening.
- 13. HIV plasma viremia between 200 and 5,000 copies/mL at screening AND at least two documented viral level  $\geq$ 200 copies/mL in the 12 months prior to screening.

At the screening visit, subjects considering enrollment in Group 2 will be advised that current guidelines recommend treatment of all individuals with HIV infection regardless of viral levels and CD4 counts.

# Reproductive Risks

Contraception: The effects of 3BNC117 and 10-1074 on the developing human fetus are unknown. For this reason, men and women of childbearing potential must agree to use adequate pregnancy prevention. This includes the use an effective method of contraception (i.e. condom with spermicide, diaphragm with spermicide, hormone-eluting IUD, hormone-based contraceptive with condom) for the study duration. Subjects should also agree to use a male or female condom while off ART. Pregnancy prevention must be practiced continuously for the duration of study participation. Females of childbearing-age must have a negative pregnancy test result prior to receiving each infusion of 3BNC117/10-1074. During the course of the study, if a female subject, or the partner of a male subject suspects or in fact becomes pregnant, the effected subject should inform the study staff immediately, as well as the woman's primary care physician.

## 4.3 Subject Exclusion Criteria

- Chronic hepatitis B, as evidenced by a positive test for hepatitis B surface antigen (HBsAg), or chronic hepatitis C virus (HCV) infection, as evidenced by a positive test for HCV RNA. Subjects with a positive test for HCV antibody and a negative test for HCV RNA are eligible.
- 2. HIV immunotherapy or vaccine(s) received within 1 year prior to screening.
- 3. Any licensed or experimental non-HIV vaccination (e.g., hepatitis B, influenza, pneumococcal polysaccharide) received within 2 weeks prior to study enrollment.
- 4. Receipt of other investigational study agent within 28 days of enrollment.
- 5. Any active malignancy that may require systemic chemotherapy or radiation therapy.
- 6. Systemic immunosuppressive medications received within 3 months prior to enrollment (Not excluded: [1] corticosteroid nasal spray or inhaler; [2] topical corticosteroids for mild, uncomplicated dermatitis; or [3] oral/parenteral corticosteroids administered for non-chronic conditions not expected to recur [length of therapy ≤10 days, with completion in ≥30 days prior to enrollment]).
- 7. History or other clinical evidence of:

- a. Significant or unstable cardiac or cerebrovascular disease (e.g., angina, congestive heart failure, recent stroke or myocardial infarction).
- b. Severe illness, malignancy, immunodeficiency other than HIV, or any other condition that, in the opinion of the investigator, would make the subject unsuitable for the study.
- 8. Active drug or alcohol use or any other pattern of behavior that, in the opinion of the investigator, would interfere with adherence to study requirements.
- 9. Pregnancy or breast-feeding at time of screening.
- 10. Documented multiclass antiretroviral drug resistance that, in the judgment of the investigator, would pose a risk of virologic failure should additional mutations develop during the study (Group 1 only).

Co-enrollment Guidelines: Co-enrollment in other trials is restricted to observational studies or those evaluating the use of a licensed medication and is subject to approval of the principal investigator (PI).

# 4.4 Justification for Exclusion of Children (Special Populations)

## **Exclusion of Children:**

Children are excluded from this study because there are insufficient data for adults regarding dosing of 3BNC117 and 10-1074 and adverse events to judge the potential risk(s) in children.

# 4.5 Enrollment of NIH Employees

NIH employees and members of their immediate families may participate in this protocol. We will follow the Guidelines for the Inclusion of Employees in NIH Research Studies and will give each employee a copy of the "NIH information sheet on Employee Research Participation."

# For NIH employees:

- NIH staff may be a vulnerable class of subjects.
- Neither participation nor refusal to participate will have an effect, either beneficial or adverse, on the participant's employment or work situation.
- The NIH information sheet regarding NIH employee research participation will be distributed to all potential subjects who are NIH employees.

- The employee subject's privacy and confidentiality will be preserved in accordance with NIH Clinical Center and NIAID policies, which define the scope and limitations of the protections.
- For NIH employee subjects, consent will be obtained by an individual independent of the employee's team. Those in a supervisory position to any employee and co-workers of the employee will not obtain consent.
- The importance of maintaining confidentiality when obtaining potentially sensitive and private information from co-workers or subordinates will be reviewed with the study staff at least annually and more often if warranted.

# 5 STUDY AGENT/INTERVENTIONS

# 5.1 Regimen

Both 3BNC117 and 10-1074 will be administered intravenously at 30 mg/kg dose level. Both study groups will receive 8 infusions of 3BNC117 and 10-1074 or placebo (Group 1) at weeks 0, 2, 4, 8, 12, 16, 20, and 24 (see Figure 1). The total duration of therapy is 24 weeks; the duration may be shorter if criteria listed in section 3.1are met.

# 5.1.1 Formulation, Packaging and Labeling

3BNC117 is provided by Celldex Therapeutics in single-use vials containing 10 ml of 3BNC117 at a 20 mg/ml concentration.

10-1074 is provided by MassBio in single-use vials containing 30 ml of 10-1074 at a 20 mg/ml concentration.

Study agent vials will be individually labeled with the name of the material, volume, lot number, concentration, storage instructions, Investigational Use Statement ("Limited by Federal Law to Investigational Use"), and manufacturer information.

# 5.2 Study Agent Storage and Handling

3BNC117 and 10-1074 should be stored at 2 - 8°C. Each 3BNC117 vial is single use only. Partially used vials or solutions must not be used to prepare another dose and instead should be handled for destruction according to Clinical Center Pharmacy regulations for the disposal of biological agents.

The site pharmacist must promptly report any storage temperature deviations outside of the normal allowance for the storage device to the PI and the investigational new drug (IND) Sponsor. The product must be quarantined in a separate area. The IND Sponsor's authorized representative will notify the site pharmacist if continued clinical use of the product is acceptable.

# 5.3 Preparation, Administration, and Dosage of Study Agent

The dose of both 3BNC117 and 10-1074 for this study is 30 mg/kg in 250 mL normal saline with overfill (20 ml). The placebo will be normal saline alone. The two antibodies will be mixed in separate bags of saline for sequential administration. To prepare an IV infusion, the pharmacist will calculate the total milligrams of each antibody needed and add the calculated total milligrams needed to a 250 ml of normal saline with 20 ml overfill using good pharmacy practices to maintain sterility. The infusion solution must be used within 3 hours. Any unused portion of an antibody vial will not be used for another subject.

The antibodies (or normal saline placebo-Group 1) will be administered sequentially by IV infusion (3BNC117/placebo first, followed by 10-1074/placebo). Each infusion will be given over 60 minutes using a volumetric pump and then flush the line with 20 ml normal saline. The total time needed to administer the dose may be longer than 60 minutes based on factors such as subject tolerance.

For women of childbearing potential, study agent administration may not proceed unless a negative pregnancy test has been obtained within the previous 24 hours. Prior to each administration, temperature, blood pressure, heart rate (pulse) and weight will be recorded and a targeted physical examination (based on signs, reported symptoms or interim medical history) may be conducted. Vital signs (temperature, blood pressure, heart rate) will be measured 30 minutes into the infusion and at the end of the infusion. Following the completion of the 10-1074/placebo infusion, the subject will be observed for 30 minutes and vital signs will be taken before the subject leaves the clinic.

## 5.3.1 Dose Adjustments and Modifications

Mild-moderate infusion related symptoms (Grade I-II), should they develop, will be managed by temporarily stopping the infusion until symptoms have resolved. For symptoms such as fever, myalgia, or urticaria, symptomatic treatment with standard doses of acetaminophen or antihistamines may be given. Once symptoms have resolved, the infusion will be restarted at half the initial rate. If symptoms recur following a reduced infusion rate and symptomatic treatment, the infusion will again be stopped until symptoms resolved and restarted at a lower rate. If the infusion cannot be completed within a 3-hour time frame because of recurrent symptoms, the infusion(s) will be discontinued for that visit.

# 5.4 Concomitant Medications and Procedures

All concomitant prescription medications taken during study participation will be recorded in CRIMSON. For this protocol, a prescription medication is defined as a medication that can be prescribed only by a properly authorized/licensed clinician. Medications to be reported in CRIMSON are concomitant prescription medications, over-the-counter medications, and non-prescription medications taken at the time of AEs (all grades).

#### 5.5 Prohibited Medications and Procedures

Treatment with immunosuppressive medications during the study is prohibited. Prohibited immunosuppressive medications do not include [1] corticosteroid nasal spray or inhaler; [2] topical corticosteroids for mild, uncomplicated dermatitis; or [3] oral/parenteral corticosteroids given for non-chronic conditions not expected to recur with a length of therapy ≤10 days.

# 6 STUDY SCHEDULE

For all the study visits, unless otherwise specified, subjects will come to the NIH Clinical Center to undergo the procedures. Unless otherwise specified, the visit window for the post-entry study visits is  $\pm$  5 days.

## 6.1 Screening

Screening may occur over the course of several contacts/visits. All inclusion and exclusion criteria must be assessed within 8 weeks before enrollment, unless otherwise specified in the eligibility criteria.

After signing informed consent, subjects will undergo the following procedures:

- Medical history and physical examination, including weight and vital signs.
- Assessment of concomitant medications
- Blood collection for:
  - HBsAg and Hepatitis C antibody serology
  - o Complete blood count (CBC) with differential, PT, activated PTT
  - Chemistry panel to include: alanine transaminase (ALT), aspartate aminotransferase (AST), alkaline phosphatase (ALP), creatinine, total and direct bilirubin, and serum albumin levels
  - Flow cytometry panel (includes CD4+ cell count)
  - Plasma HIV and HCV viral RNA levels
- Storage of PBMCs, serum and plasma (if needed for repeat HIV antibody testing or viral RNA levels)
- Urinalysis
- Serum or urine pregnancy test for women of child-bearing potential
- Electrocardiogram (ECG)

#### 6.2 Enrollment/Baseline

The enrollment visit may take place over 2 visits to accommodate the baseline pre-treatment apheresis procedure. The first dose of 3BNC117 and 10-1074 or (for Group-1) normal saline placebo will be administered at this visit, and enrollment is defined as the day of receipt of the first study infusions.

Subjects will undergo the following procedures (prior to the first dose of the study antibodies or saline placebo):

- Medical history and physical examination, including weight and vital signs
- Ophthalmologic Exam (within 8 weeks prior to first study infusion)
- Assessment of concomitant medications
- HIV transmission risk behavior assessment and counseling
- Leukapheresis (optional) for research studies
- Blood collection for:
  - Flow cytometry panel (includes CD4+ cell count)
  - o Plasma HIV viral RNA levels
  - HLA typing (if not already on file)

- Storage of plasma, serum and PBMCs
- o CBC with differential
- Chemistry panels, to include: ALT, AST, ALP, creatinine, total and direct bilirubin, and serum albumin levels
- Serum or urine pregnancy test (for women of child-bearing potential-obtained within 24 hours prior to infusion)

#### 6.3 ATI/Treatment Phase

Subjects will be administered 3BNC117 and 10-1074/ placebo on study day 0. All subjects in Group 1 will discontinue their ART regimen after study day 3. Subsequent infusions of 3BNC117 and 10-1074/placebo will occur at study Week 2, 4, and every four weeks thereafter until study Week 24 for a total of 8 doses (see Figure 1).

Storage of plasma, serum, and cells may be done at study day 0, Week 2, 4 and every 2 weeks thereafter for the duration of the ATI-Treatment phase. Flow cytometry (including CD4 count) and Plasma HIV viral RNA levels will be done every 2 weeks for the duration of the ATI-Treatment Phase. HIV genotype will be obtained on all samples with HIV viral levels >1,000 copies/ml. For select subjects residing outside the local (Bethesda, MD) area, blood samples for blood draw only visits, may be collected at their local clinics or Quest Diagnostics and sent to the NIH Clinical Center for testing. Samples collected at clinics or at Quest may be labeled with a coded identifier, gender, and date of birth, as required by the local facility.

At infusion visits, the following will be done in addition to the flow cytometry panel and plasma HIV viral level:

- Interval medical history and a targeted physical examination, including weight, vital signs, and a symptom-directed evaluation based on symptoms or complaints reported by each subject
- Assessment of concomitant medications
- Assessment of any new or unresolved AEs/intercurrent illnesses
- Blood collection:
  - CBC with differential
  - Chemistry panels, to include: ALT, AST, ALP, creatinine, total and direct bilirubin, and serum albumin levels
- Serum or urine pregnancy test for women of child-bearing potential (results must be reviewed prior to infusion)
- Optional leukapheresis for research studies will be done at Week 0, 16 and within +/14 days of the week 24 infusion
- HIV transmission risk behavior assessment and counseling

For non-infusion visits, participants unable to return to the NIH CC during the COVID-19 epidemic/pandemic due to travel restrictions, blood samples may be collected at their local clinics or Quest Diagnostics and sent to the NIH CC for testing which will include; CBC with differential, plasma HIV viral level, and flow cytometry. Chemistry panels may be run at Quest Diagnostics laboratories and the results sent to the NIH Study team. A study provider (Nurse Practitioner, Physician's Assistant, or Physician) will contact participants by phone and obtain an interval medical history.

After the final infusion at week 24, all subjects in Group 1 will continue to have CD4 counts and plasma viral levels monitored every 2 weeks and will be seen every 4 weeks until they meet criteria to restart ART. If a subject in Group 1 meets criteria for ending ATI prior to Week 24, no further infusions will be given; the subject will be instructed to restart ART and continue to be followed as described in Section 6.4.

If a subject in Group 1 has not met criteria to restart ART at Week 64 but has a sustained viral level >40 copies/ml (but <1,000 copies/ml), s/he will be advised to restart ART. Subjects with sustained VL <40 copies/ml at Week 64 may elect to remain off ART until viremia becomes detectable. For such subjects, CD4 counts and plasma viremia will be monitored every 4 weeks until viremia is detected; at which time they will be instructed to restart ART and be followed as described in Section 6.4 below.

If a subject in Group 2 meets criteria for ending 3BNC117/10-1074 infusions prior to Week 24, they will continue to be followed as described in Section 6.4.

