# 6.4 Follow-up Phase

Group 1: Subjects in Group 1 will enter the follow-up Phase when they meet criteria to re-start ART and will be seen 4, 12, and 24 weeks after restarting ART to ensure viral suppression has been achieved.

Group 2: Subjects in Group 2 will enter the follow-up Phase after their final 3BNC117/10-1074 infusion and will be seen 4, 12, and 24 weeks after the last antibody infusion.

At these visits, subjects in both groups will undergo the following procedures:

- Interval medical history and a targeted physical examination, including weight, vital signs, and a symptom-directed evaluation based on symptoms or complaints reported by each subject
- Assessment of any new or unresolved AEs or intercurrent illnesses
- Blood collection for:
  - CBC with differential
  - Chemistry panels, to include: ALT, AST, ALP, creatinine, total and direct bilirubin, and serum albumin levels
  - Flow cytometry panel (includes CD4+ T cell count)
  - Plasma HIV viral level
  - HIV genotype (Group 1; if viral level is >1,000 copies/ml)
  - Storage of serum, plasma and PBMCs

Subjects in Group 2 will also have optional blood draw visits for CD4 counts, plasma viral level, and storage at 2, 6, 8, 10, 16, and 20 weeks after the last antibody infusion which may be drawn at NIH or offsite.

For participants who are unable to return to the NIH CC during the COVID-19 pandemic due to travel restrictions, blood samples may be collected at their local clinics or Quest Diagnostics and sent to the NIH CC for testing which will include; CBC with differential, plasma HIV viral level, and flow cytometry. Chemistry panels may be run at Quest Diagnostics laboratories and the

results sent to the NIH Study team. A study provider (Nurse Practitioner, Physician's Assistant, or Physician) will contact participants by phone and obtain an interval medical history.

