## Appendix B continued:

## **Group 1 Extended ATI Phase**

Study Point		Wk 26	Wk 28	Wk 30	Wk 32	. Wk 34	Wk 36	Wk 38	Wk 40	Wk 42	Wk 44	Wk 46	Wk 48	Wk 50	Wk 52	Wk 54	Wk 56	Wk 58	Wk 60	Wk 62	Wk 64	If VL>40, but <1000 at Wk 64, will be advised to restart ART and will move to the Follow up Phase	If VL <40 at week 64, may remain off ART and have CD4 and VL drawn every 4 weeks till viremia is dectected.
PROCEDURES / CONSULTS:																							
Physical Exam			х		Х		Х		Х		х		х		х		х		х		х		
LABS:																							
CBC			х		х		х		Х		х		х		х		х		х		х		
RESEARCH LABS:																							
(WHBL) Flow Cytometry with CD4+		х	х	x	х	х	х	х	x	x	х	х	х	х	х	х	х	х	х	х	х		x
(Abbott HIV RTPCR) HIV																							
Viral Load		x	х	x	х	x	х	х	х	х	x	х	х	х	x	х	x	х	х	x	х		х
Plasma Storage		х	х	х	Х	Х	Х	Х	Х	Х	х	Х	х	Х	х	Х	х	Х	х	х	Х		х
Serum Storage		х	х	х	Х	Х	Х	Х	Х	Х	х	Х	х	Х	х	Х	х	Х	х	х	х		Х
PBMC Storage		х	Х	х	Х	х	х	х	х	Х	Х	х	Х	Х	х	х	Х	Х	х	Х	Х		х
Blood volume will not exceed	curro	ot NIILI li	mits as a	dofinad	by NAAS	05.0																	

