# Appendix B continued: Group 1 Follow Up Phase

Study Point		F/U Wk 4	F/U Wk 12	F/U Wk 24
Protocol Visit Date				
PROCEDURES / CONSULTS				
Apheresis	2L			Х
NIH Visit		Χ	Х	Х
Medical History, Targeted PE,				
Sympton Directed Eval, VS, Wgt, Medication Review		X	X	Х
Assess AEs / Intercurrent		.,	.,	.,
illnesses  LABS:		Х	Х	Х
Pregnancy (POC)- Result must be Neg Before Apheresis				Х
CBC with Diff		Х	Х	Х
Chem: ALT, AST, AlK Phos,				
Creatinine, Total and Direct				
Bili, Serum Albumin		Χ	Х	Χ
RESEARCH LABS:				
(WHBL) Flow Cytometry with		.,	.,	.,
CD4+		Х	Х	Х
(Abbott HIV RTPCR) HIV Viral				
Load		Х	Х	Х
HIV Genotype (Group One: If				
VL >1000)		Х	Х	Х
Plasma Storage		Χ	Х	Х
Serum Storage		Х	Х	Х
PBMC Storage		Х	Х	Х
ONLY If PT Cannot apherese	30 mL Hep Syringe			X
ONLY If PT Cannot apherese	50 mL Hep Syringe			Х
Blood volume will not excee	d current NIH limi	ts as define	d by MAS-95	 

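### After the last infusion at week 24, Group 1 subjects still off ART have no scheduled chemistry panel until 4 weeks after ART restart, while Group 2 has one 4, 12 and 24 weeks after its last infusion

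*Combined protocol and SAP*

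**What the plan says.** Section 5.1 gives one regimen for the whole trial: "Both study groups will receive 8 infusions of 3BNC117 and 10-1074", or placebo in Group 1, at weeks 0, 2, 4, 8, 12, 16, 20 and 24.

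Section 6.3 lists the procedures for infusion visits. The list includes a chemistry panel (ALT, AST, ALP, creatinine, bilirubin, albumin) and "Assessment of any new or unresolved AEs/intercurrent illnesses". It applies for the last time at week 24.

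For Group 1 after week 24, Section 6.3 says that subjects "will continue to have CD4 counts and plasma viral levels monitored every 2 weeks and will be seen every 4 weeks" until they meet the restart criteria. It gives no procedure list for those visits. The Appendix B sheet headed "Group 1 Extended ATI Phase" has rows for physical examination and CBC every 4 weeks from week 28 to week 64, and for CD4, viral load and sample storage every 2 weeks. It has no chemistry row and no AE-assessment row. For subjects who stay off ART after week 64, it marks only CD4, viral load and storage.

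Section 6.4 provides chemistry and AE assessment at follow-up visits in both groups but starts the clock differently. Group 1 subjects "will be seen 4, 12, and 24 weeks after restarting ART". Group 2 subjects "will be seen 4, 12, and 24 weeks after the last antibody infusion". The Appendix B sheets agree: the "Group 1 Follow Up Phase" sheet and its Group 2 counterpart both carry the two items at follow-up weeks 4, 12 and 24.

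**The concern.** The primary endpoint (Section 3.2.1) is the rate of grade 3 or higher AEs probably or definitely related to the study agents. Section 14 pools 30 antibody recipients from both groups to estimate it. A liver or renal abnormality without symptoms is found only if someone tests for it. The week-24 panel belongs to the same visit as infusion 8, so it cannot show what follows that infusion. In Group 2 the next panel comes 4 weeks later. In a Group 1 subject who is doing well off ART, it comes at a time set by viral rebound rather than by exposure to the antibodies.

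Two kinds of unevenness follow. Group 1 and Group 2 recipients enter one safety denominator with different laboratory follow-up after the last dose. Within Group 1, the arm expected to stay off ART longer, the antibody arm, has the longer stretch without chemistry.

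**Working it through.** **Plan's own figures.** Table 1: 1 - (1 - 0.10)^30 = 0.958, as stated; the other five entries also reproduce. Table 2 reproduces as the exact power of a two-sided Fisher test at the 5% level with 15 per arm (0.872 at a restart probability of 0.20, 0.680 at 0.30). The plan does not name the test or the level, so both are assumed. Neither table is in dispute.

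**Schedules side by side, from infusion 8 at week 24**

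| | Group 1, still off ART | Group 2 |
|---|---|---|
| Physical examination, CBC | every 4 weeks, weeks 28-64 | 4, 12, 24 weeks after last infusion |
| Chemistry panel | none until 4 weeks after ART restart | 4, 12, 24 weeks after last infusion |
| AE-assessment item | none listed until 4 weeks after ART restart | 4, 12, 24 weeks after last infusion |

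Each of infusions 1-7 is followed by another infusion visit, with chemistry, after 2, 2, 4, 4, 4, 4 and 4 weeks. For these subjects, infusion 8 is the only one with no panel at a fixed time after it.

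**Subjects affected.** Inputs: 15 per Group 1 arm (Section 3.1); restart probabilities 0.20-0.30 (antibody) and 0.80 (placebo) (Section 14).
- Antibody arm: 15 × (1 - 0.30) = 10.5 to 15 × (1 - 0.20) = 12.
- Share of the 30 in Table 1: 10.5/30 = 35% to 12/30 = 40%.
- Placebo arm: 15 × (1 - 0.80) = 3.

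**Interval from the week-24 panel to the next one** = (restart week + 4) - 24.
- Restart at week 28: 8 weeks.
- Restart at week 40: 20 weeks.
- Restart at week 52: 32 weeks.
- Restart at week 64: 44 weeks.
- Still off ART after week 64: no fixed limit.
- Group 2: 4 weeks.

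The subjects counted above have not restarted by week 28, so 8 weeks is their minimum. Someone who restarts at week 26 has 26 + 4 - 24 = 6 weeks but is not in the count.

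**Residual exposure.** Half-lives are 18 days (3BNC117) and 24 days (10-1074), reported in Section 1.1.3.3 for HIV-uninfected people. Simple exponential decay is assumed. Fraction of infusion 8 left = 0.5^(days/half-life).
- Week 28 (28 days): 0.5^(28/18) = 0.340 and 0.5^(28/24) = 0.445.
- Week 36 (84 days): 0.039 and 0.088.
- Week 48 (168 days): 0.0016 and 0.0078.

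Residual exposure is therefore concentrated in roughly the first 12 weeks of the gap.

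**The case against.** **AEs are still collected.** A reader might infer that Group 1 has no AE collection after week 24. The documents do not support that. Section 12.3 requires all AEs from the first infusion through follow-up to be recorded. Section 12.1 has them elicited by questioning and examination at designated visits, and these subjects are examined every 4 weeks to week 64. Symptomatic and haematological events can be found there. The missing AE row is thus secondary; the missing chemistry is what remains.

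**The sheet may be abbreviated.** The Appendix B screening sheet shows no ALT, AST or ALP, although Section 6.1 requires them. The COVID provision in Section 6.3 contemplates chemistry at non-infusion visits and requires an interval history by telephone. The omission may well be unintended. But that provision only permits chemistry, and only for travel-restricted participants. Section 7.2.1 refers back to Section 6, which schedules none here. The six months of evaluations in Section 12.10 apply to premature discontinuation, not to subjects who complete eight infusions.

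**Earlier safety data are reassuring.** In Appendix A, 6 of 48 AEs were bilirubin or transaminase findings (2 related, 4 not). The two related ones were mild, and the two severe ones were judged unrelated, so none would have met this trial's primary endpoint. Sections 1.1.3.1 and 1.1.3.2 report no related grade 3 events with either antibody alone, though with fewer doses. This argues against a high late event rate. It also shows that chemistry is a route by which AEs were found.

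**Table 1 does not fall by a known amount.** A reader might remove the affected subjects from the 30 and recompute the 0.958. That would require an event that arises only in the gap, resolves before the panel after restart, and is missed at every examination. Nothing in the documents supports that combination.

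**The different anchors have a purpose.** Section 6.4 ties Group 1 follow-up to ART restart in order to confirm re-suppression. That explains the virological visits but gives no reason to omit chemistry after the last infusion.

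**Conclusion.** The gap is real and should be closed. It does not invalidate the primary safety analysis. Followed as written, the plan schedules no chemistry after infusion 8 for about 10.5-12 Group 1 antibody recipients (35-40% of the pooled 30) and about 3 placebo subjects until 4 weeks after ART restart. That is 8 to 44 weeks from the week-24 panel for restart at weeks 28 to 64, and open-ended beyond, against 4 weeks in Group 2. The early part of the gap matters most, because that is when appreciable antibody remains.

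The counts rest on the plan's assumed restart probabilities and on those subjects completing infusion 8 and staying in the study. The exposure figures rest on half-lives from HIV-uninfected people and on exponential decay. The consequence is uneven laboratory ascertainment between groups and between the Group 1 arms. The number of events lost cannot be estimated from the documents, and Group 2 completers do supply late chemistry data under the same regimen. Confidence is medium, mainly because the flow sheet may be an incomplete statement of what was intended.

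**What to change.** Reconcile the Group 1 extended ATI schedule (Section 6.3 and its Appendix B sheet) with the post-infusion safety schedule in Section 6.4. The simplest way is to carry the chemistry and AE-assessment rows already used on the other Group 1 sheets into existing 4-weekly visits. Weeks 28, 36 and 48, for example, match Group 2's checks at 4, 12 and 24 weeks. If the difference between the groups is intended, say so and give the reason.

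Cost for those three visits: 3 × (10.5 + 3) = 40.5 to 3 × (12 + 3) = 45, so about 41-45 extra chemistry tubes. That is an upper limit, because some subjects will restart ART before week 36 or 48. These visits already include an examination and a blood draw, so no visit is added.
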